7.1.3. Reporting of Adverse Events

Guidelines for reporting of adverse events provided by NICHD, UCSF Committee for Human Research (CHR), and the Food and Drug Administration (FDA) in the U.S. and the Makerere University IRB (SOMREC), and National Drug Authority (NDA) in Uganda will be followed as summarized in Table 6 below.

Table 6. Guidelines for reporting adverse events

Institution	Type of Adverse Events	When to Report
NICHD	
 • Definitely, Probably, or Possibly related AND Serious or Unexpected 	
 • Within 10 working days of awareness
UCSF-CHR	External [off-site] adverse event that UCSF PI determines: 
 • changes the study risks or benefits, OR 
 • necessitates modification to the CHR-approved consent document(s) and/or the CHR-approved application/protocol 	
 • Within 10 working days of PI's awareness
MU-SBSREC	
 • All Serious and Unexpected events irrespective of relationship; 	
 • Fatal or life-threatening events within 3 working days of awareness • All other SAEs within 7 calendar days
NDA	
 • All Serious and Unexpected events irrespective of relationship 	
 • Within 7 calendar days of awareness
FDA	
 • Definitely, Probably or Possibly related AND BOTH Serious* AND Unexpected[‡] 	
 • For fatal or life-threatening events, by telephone or fax within 7 calendar days of first awareness • All other reportable events within 15 calendar days of first awareness

Serious Adverse Event (SAE) is any AE that results in any of the following outcomes:

- Death,
- Life-threatening adverse experience.
- Inpatient hospitalization or prolongation of existing hospitalization,
- Persistent or significant disability/incapacity,
- Congenital anomaly/birth defect, or cancer, or
- Any other experience that suggests a significant hazard, contraindication, side effect or precaution that may require medical or surgical intervention to prevent one of the outcomes listed above,
- Event occurring in a gene therapy study

- Event that changes the risk/benefit ratio of the study.

Unexpected Adverse Event An adverse event is defined as being unexpected if the event exceeds the nature, severity, or frequency described in the protocol, consent form and investigator brochure (when applicable). An unexpected AE also includes any AE that meets any of the following criteria:

- Results in subject withdrawal from study participation,
- Due to an overdose of study medication, or
- Due to a deviation from the study protocol

8. STATISTICAL CONSIDERATIONS

8.1. Hypothesis 1

We will test the hypothesis that pregnant women who receive IPTp with either 3 dose DP or monthly DP will have a lower risk of placental malaria defined by histopathology compared to those who receive 3 doses of SP. Secondary outcomes will include maternal and fetal clinical outcomes. We will also compare the two different dosing strategies of DP.

8.1.1. Primary Outcome

The primary outcome will be the prevalence of placental malaria based on placental histopathology and dichotomized into any evidence of placental infection (parasites or pigment) vs. no evidence of placental infection. We will also evaluate placental malaria defined by histopathology as a categorical variable (active-acute, active-chronic, and past infection) based on the criteria developed by Rogerson et al.⁸⁰

8.1.2. Secondary Outcomes

Secondary outcomes are summarized in Table 7 below.

Table 7. Secondary outcomes

Secondary outcome	Definition
Placental parasitemia	Proportion of placental blood samples positive for parasites by microscopy or PCR
Maternal malaria	Any treatment for malaria
Composite birth outcome	Congenital malformations, late spontaneous abortion (<28 weeks), LBW (<2500g), still birth (fetal demise ≥28 weeks), congenital anomaly, or preterm delivery (<37 weeks).

Incidence of adverse events	Adverse events stratified by type, severity score and relationship to study drugs
Prevalence of anemia	Proportion of routine hemoglobin measurements < 10 g/dL & < 8 g/dL
Prevalence of asymptomatic parasitemia	Proportion of routine monthly samples positive for parasites by PCR

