8.1.3. Analyses

An intention-to-treat approach to all analyses will be used, including all study participants randomized to therapy and including all follow-up time until the study participants complete the study or early study termination regardless of whether the intervention was stopped due to an adverse event.

Primary analysis. We will compare the prevalence of placental malaria defined by histopathology at birth between the study arms using the Chi-Square test for all pair-wise comparisons. We will explore for any differences of potential confounders between the treatment arms and if necessary adjust our analysis using multivariate logistic regression.

Secondary analyses. We will compare the prevalence of placental parasitemia and our composite birth outcome using the Chi-Square test. We will compare the incidence of maternal malaria and adverse events using Poisson or negative binomial regression models. The Poisson models will include the logarithm of the follow-up time as an offset. We will translate the fitted coefficients and their confidence bounds into percentage effects with the formula $100 * [\exp(\text{coefficient}) - 1]$. This approach is closely related to exponential survival models for analyzing events per follow-up time, but is better able to adjust for violated assumptions. Testing for overdispersion in the Poisson regression can detect violations of these assumptions, and variances can be adjusted accordingly to produce valid p-values and confidence interval. If significant deviations from required distributions in study data are detected, we will employ negative-binomial or zero-inflated negative-binomial models to account for the observed pattern of data. We will compare the prevalence of maternal anemia and asymptomatic parasitemia using generalized estimating equations with adjustments for repeated measures in the same study participant. If necessary, multivariate analyses will be performed to adjust for potential confounders and effect modifiers.

8.2. Hypothesis 2

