8.2.3. Analyses

An intention-to-treat approach to all analyses will be used, including all infants born to mothers assigned to receive IPTp with 3 dose DP or monthly DP and including all follow-up time until the

study participants reach 24 months of age or early study termination regardless of whether the intervention was stopped due to an adverse event.

Primary analysis. We will compare the incidence of malaria using Poisson or negative binomial regression models as described in section 9.1.3. In necessary, multivariate analyses will be performed to adjust for potential confounders and effect modifiers.

Secondary analyses. We will compare the incidence of complicated malaria, hospitalizations, and adverse events using Poisson or negative binomial regression models as described in section 9.1.3. We will compare the prevalence of anemia, asymptomatic parasitemia, and gametocytemia using generalized estimating equations with adjustments for repeated measures in the same study participant. In necessary, multivariate analyses will be performed to adjust for potential confounders and effect modifiers.

8.3. Hypothesis 3

We will test the hypotheses that A) infants born to mothers randomized to receive IPTp with 3 dose DP or monthly DP will have a lower incidence of malaria during the first 24 months of life compared to infants born to mothers who were randomized to receive IPTp with 3 doses of SP, and, B) infants randomized to receive monthly DP between 2-24 months of age will have a lower incidence of malaria between 24-36 months of age after the intervention is stopped compared to infants randomized q 3 monthly DP between 2-24 months of age. For hypothesis 3A, we will only include infants randomized to receive q 3 monthly DP during infancy. For hypothesis 3B, we will also explore for interaction with the intervention given during pregnancy.

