8.4. Sample size and power

The number of pregnant women enrolled and the number of study participants reaching the various endpoints will determine the sample sizes for each of the primary outcomes of our study aims (Table 9). The primary determinant of our target sample size was based on testing hypotheses 3 given that the magnitude of differences anticipated for this hypothesis would be smaller than those anticipated for hypothesis 1 and 2. We conservatively estimate that 90% of pregnant women enrolled will reach the primary study endpoint and we will lose 5% of follow-up time per year in the infants. The minimum relative differences detectable for the primary outcomes of the 3 hypotheses given our estimated sample sizes are summarized in Table 10 below. For hypotheses 1, we will be powered to detect a 33% relative difference in the prevalence of placental malaria in the 3 dose DP arm or the monthly DP arm compared to the 3 dose SP arm assuming a prevalence of placental malaria of 62% in the 3 dose SP arm based on prior data. We will also be powered to detect a 41-70% relative difference in the prevalence of placental malaria in the monthly DP arm compared to the 3 dose DP arm assuming a prevalence of placental malaria in the 3 dose DP arm ranging from 20-50%. For hypothesis 2, we will be powered to detect an 18-23% relative difference in the incidence of malaria between 0-24 months of age in the monthly DP arm compared to the q 3 monthly DP arm assuming an incidence of malaria in the q 3 monthly DP arm ranging from 3-5 episodes PPY. For hypothesis 3A, we will be powered to detect a 22-28% relative difference in the incidence of malaria between 0-24 months of age among children assigned to receive q 3 monthly DP when comparing those born to mothers who received 3 dose SP to those born to mothers who received 3 dose DP or monthly DP assuming an incidence of malaria in the control group ranging from 3-5 episodes PPY. For hypothesis 3B, we will also be powered to detect a 16-21% relative difference in the incidence of malaria between 24-36 months of age among children assigned to receive monthly DP during infancy compared to those who received q 3 monthly DP

during infancy assuming an incidence of malaria in the control group ranging from 3-5 episodes PPY.

Table 9. Intervention arms during pregnancy and infancy

Study populations	Intervention arms				
	3 doses of SP	3 doses of DP		monthly DP	

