Assigned treatment arms in pregnant women	3 doses of SP	3 doses of DP		monthly DP	
Estimated number of pregnant women enrolled	100	100		100	
Estimated number with placental outcomes	90	90		90	
Assigned treatment arms in infants	q 3 monthly DP	q 3 monthly DP	monthly DP	q 3 monthly DP	monthly DP
Estimated number of infants enrolled	90	45	45	45	45
Estimated number of infants reaching 24 months of age	81	41	41	41	41

Table 10. Minimum relative differences in outcomes detectable given estimated effective sample sizes

Hypothesis	Analysis population	Control group and estimated sample size	Comparison group and estimated sample size	Estimated outcome measure in control group	Minimum relative difference detectable*
1	Pregnant women with placental malaria measured at birth	3 dose SP (n=90)	3 dose DP or monthly DP (n=90 each)	Prevalence of placental malaria = 62%	33%
		3 dose DP (n=90)	monthly DP (n=90)	Prevalence of placental malaria = 20-50%	41-70%
2	Infants 0-24 months of age born to mothers assigned to receive IPTp with 3 dose DP or monthly DP	Infants assigned q 3 monthly DP (n=90)	Infants assigned monthly DP (n=90)	Incidence of malaria = 3-5 episode PPY	18-23%
3	Infants 0-24 months of age randomized to q 3 monthly DP	Infants of mothers assigned 3 dose SP (n=90)	Infants of mothers assigned 3 dose DP or monthly DP (n=45 each)	Incidence of malaria = 3-5 episodes PPY	22-28%
	Infants 24-36 months of age after chemoprevention stopped	Infants assigned q 3 monthly DP (n=162)	Infants assigned monthly DP (n=81)	Incidence of malaria = 3-5 episodes PPY	16-21%

* Relative difference = (estimated outcome in control arm – estimated outcome in the comparison arm) / estimated outcome on the control arm (two-sided alpha = 0.05, power = 80%).

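### Routine hemoglobin is tested for efficacy only as proportions below 10 and 8 g/dL, with no commitment to adjust for the women's enrolment value; adding mean hemoglobin would be a cheap gain

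*Protocol*

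**What the plan says.** Table 7 (section 8.1.2, women) and Table 8 (section 8.2.2, infants) define prevalence of anaemia identically: "Proportion of routine hemoglobin measurements < 10 g/dL & < 8 g/dL".

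Section 8.1.3 gives the analysis for women: "We will compare the prevalence of maternal anemia and asymptomatic parasitemia using generalized estimating equations with adjustments for repeated measures in the same study participant". Section 8.2.3 does the same for infants: "We will compare the prevalence of anemia, asymptomatic parasitemia, and gametocytemia using generalized estimating equations with adjustments for repeated measures in the same study participant". Both sections allow multivariate adjustment if it proves necessary, without naming a covariate.

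Hemoglobin comes from the CBC. Women have one at enrolment (section 4.4) and every 8 weeks afterwards; children have one every 16 weeks (sections 6.5 and 6.10.2). Its only other analytic use is as a graded laboratory adverse event (Appendix J), which enters the adverse-event outcomes of Tables 7 and 8.

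Section 8.4 gives detectable differences for the primary outcomes only. It states no power, expected prevalence, mean, SD or within-person correlation for hemoglobin.

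**The concern.** Cutting a continuous measurement at a threshold discards the distance from that threshold. If an intervention moves hemoglobin generally, the proportion below a cut is a less efficient test than the mean, and the loss grows as the cut moves into the tail. With about 90 participants per arm there is little power to spare.

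The protocol's own history suggests that the margin is thin. In the earlier chemoprevention trial (section 1.2), 393 children in four arms, or about 98 per arm, gave 47% protection against moderate-severe anaemia for monthly DP, with a 95% CI of 1–72% and p=0.04. The comparator there was no chemoprevention. Here the infant contrast is monthly against 3-monthly DP, two active regimens, so the difference may well be smaller. The cut used in that trial is not stated, so this is context and not an input.

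The women's enrolment hemoglobin is collected from everyone and should predict later values, yet no analysis is committed to using it. At stake is an inconclusive anaemia comparison where data already in hand might have given a clearer answer. A mean-hemoglobin analysis added after unblinding would look post hoc.

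**Working it through.** **Step 1: reproduce the plan's nearest figure.** Nothing is stated for anaemia, so I used Table 10, hypothesis 1 ("assuming a prevalence of placental malaria of 62% in the 3 dose SP arm based on prior data"; "two-sided alpha = 0.05, power = 80"%; n=90 per arm).

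Power = Φ{[|p₁−p₂| − 1.96√(2p̄(1−p̄)/n)] / √[(p₁(1−p₁)+p₂(1−p₂))/n]}.

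With p₁=0.62 and p₂=0.62×0.67=0.415: (0.2046−0.1460)/0.0729=0.80, so power is 78.9%. Likewise 50% with a 41% reduction gives 80.8%, and 20% with a 70% reduction gives 80.3%. Table 10 reproduces. It also shows that a single binary outcome at 20% prevalence needs a 70% relative reduction at this arm size.

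**Step 2: inputs for hemoglobin.** From the protocol: 90 per arm; about 6 routine values per child to 24 months (104 weeks/16); about 3 post-drug values per woman; GEE with repeated measures. *Assumed*, because the protocol is silent: normal hemoglobin, control mean 10.0–11.5 g/dL, SD 1.2–1.5, within-person correlation ρ 0.3–0.5, and a uniform shift set so that the continuous analysis has 80% power (0.32–0.51 g/dL over the range).

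**Step 3: one setting by hand.** Infants, m=6, mean 10.5, SD 1.5, ρ=0.5.

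- Continuous: variance factor [1+(m−1)ρ]/m = 3.5/6 = 0.583. SE = 1.5√(0.583×2/90) = 0.171. Shift = (1.96+0.84)×0.171 = 0.48 g/dL.
- Below 10: control Φ(−0.333)=0.369, treated Φ(−0.652)=0.257, difference 0.112. The correlation of the binary indicators, from the bivariate normal, is 0.33 and 0.31. Person-level variances p(1−p)[1+5ρ_b]/6 are 0.102 and 0.081. SE = √(0.183/90) = 0.045. Power = Φ(2.49−1.96) = 70%.
- Below 8: proportions 0.048 and 0.024, SE 0.0157. Power = Φ(1.55−1.96) = 34%.

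**Step 4: simulation over the range.** 4,000 trials per setting; the binary analysis compares person-level proportions with a robust variance, which is equivalent to an independence GEE.

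| Setting | Continuous | <10 | <8 |
|---|---|---|---|
| Infants, 6 values, mean 10.5, SD 1.5, ρ 0.5 | 80% | 69% | 35% |
| Infants, 6 values, 11.0, 1.2, 0.3 | 79% | 58% | 8% |
| Women, 3 values, 10.5, 1.3, 0.4 | 82% | 66% | 20% |
| Women, 3 values, 10.0, 1.5, 0.5 | 80% | 68% | 39% |
| Women, 3 values, 11.5, 1.2, 0.5 | 81% | 43% | <1% |

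Over the whole assumed range, infants have 50–72% at <10 and 0–47% at <8; women have 42–69% and 0–39%. The near-zero values arise where almost nobody is below 8: mean 11.5 with SD 1.2 gives Φ(−2.92), about 0.2%.

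**Step 5: cross-check by prevalence.** Applying the Step 3 formula with 4–6 values per person and ρ 0.3–0.7, power at <10 is about 42–48% if control prevalence is 10%, 56–61% if 20%, and 69–73% if 50%.

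**Step 6: sensitivity to the effect.** In the Step 3 setting, a shift of 0.24 gives 29% (continuous) against 24% (<10), and a shift of 0.72 gives 99% against 96%. So the gap is widest near the shift chosen here. If treatment only lowers the share of anaemic participants (25% to 8%, drawn from N(9, 0.8), the rest from N(11.5, 1.0), one value each), the <10 cut has 65% power and the mean 56%. With the rest at N(11.0, 1.0), both have about 46%.

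**Step 7: enrolment adjustment in women.** Under the same uniform-shift model, adjusting for enrolment hemoglobin adds roughly 6–14 points to the <10 analysis. The gain shrinks as the within-person correlation falls.

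**The case against.** The strongest reply is that nothing here is wrong. Anaemia prevalence is the clinically meaningful outcome: section 2.2 names it for infants and Table 7 lists it for women. The tables define it, the analysis sections follow the definition, and no power is claimed for it. A supportive mean-hemoglobin model could sit in a statistical analysis plan that is not shown. All of this stands. It makes the point a suggestion and not the correction of an error.

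The protocol's evidence on DP also concerns low hemoglobin: the 47% protection cited above, and 24 against 56 grade 3–4 anaemia events in Table 14. That fits an effect in the tail, where Step 6 shows the cut can do as well as the mean or better. This stands too, and is the reason not to drop the prevalences.

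Four stronger readings are tempting, and the protocol does not support them:

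- *The plan loses a fixed 8–38 points of power.* Those differences (80−72 and 80−42) follow from assumed hemoglobin inputs and a shift chosen for 80% continuous power. They are not a property of the plan or a bound.
- *Repeated measurements are collapsed.* GEE keeps them; only the hemoglobin scale is dichotomised.
- *Hemoglobin is analysed nowhere else, with the same cuts for women and infants throughout.* It is also graded in Appendix J with separate adult and paediatric limits.
- *Enrolment hemoglobin is excluded.* Section 8.1.3 permits adjustment; it does not commit to this covariate.

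What survives is narrower. Neither scale is better under every mechanism, and the protocol plans only one of them for efficacy.

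**Conclusion.** The point holds as a minor efficiency improvement on a secondary outcome. Routine hemoglobin is tested for efficacy only through two proportions, and the women's enrolment value is not a committed covariate. With normal hemoglobin, the Step 2 ranges and a uniform shift detectable with 80% power on the continuous scale, the <10 g/dL analysis has roughly 42–72% power and the <8 g/dL analysis roughly 0–47%. Every hemoglobin input is an assumption. At smaller or larger shifts the gap narrows, and if the effect lies only in the anaemic tail the advantage can disappear or reverse.

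A reader might infer that mean hemoglobin should replace the prevalences. The protocol does not support that: prevalence is the outcome it names, and its prior evidence lies in the low range. The case is for planning both.

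**What to change.** Keep the proportions below 10 and below 8 g/dL as the named secondary outcome. In Tables 7 and 8 and sections 8.1.3 and 8.2.3, add beside them the mean difference between arms in routine post-enrolment hemoglobin (g/dL), with a confidence interval, from the planned GEE with identity link and visit week (women) or age (children) as a factor.

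In women, adjust both the mean and the prevalence analyses for enrolment hemoglobin. If the prevalence model uses a logit link, the adjusted odds ratio is conditional on that covariate, so tabulate the raw prevalences as well. If the statistical analysis plan already specifies these analyses, a cross-reference is enough.

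The cost is one line in each table and a sentence in each analysis section. No new data, procedures or participants are needed. The small downside is one further secondary analysis in each phase, on a scale less directly clinical than a prevalence.

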8.1.3. Analyses

An intention-to-treat approach to all analyses will be used, including all study participants randomized to therapy and including all follow-up time until the study participants complete the study or early study termination regardless of whether the intervention was stopped due to an adverse event.

Primary analysis. We will compare the prevalence of placental malaria defined by histopathology at birth between the study arms using the Chi-Square test for all pair-wise comparisons. We will explore for any differences of potential confounders between the treatment arms and if necessary adjust our analysis using multivariate logistic regression.

Secondary analyses. We will compare the prevalence of placental parasitemia and our composite birth outcome using the Chi-Square test. We will compare the incidence of maternal malaria and adverse events using Poisson or negative binomial regression models. The Poisson models will include the logarithm of the follow-up time as an offset. We will translate the fitted coefficients and their confidence bounds into percentage effects with the formula $100 * [\exp(\text{coefficient}) - 1]$. This approach is closely related to exponential survival models for analyzing events per follow-up time, but is better able to adjust for violated assumptions. Testing for overdispersion in the Poisson regression can detect violations of these assumptions, and variances can be adjusted accordingly to produce valid p-values and confidence interval. If significant deviations from required distributions in study data are detected, we will employ negative-binomial or zero-inflated negative-binomial models to account for the observed pattern of data. We will compare the prevalence of maternal anemia and asymptomatic parasitemia using generalized estimating equations with adjustments for repeated measures in the same study participant. If necessary, multivariate analyses will be performed to adjust for potential confounders and effect modifiers.

8.2. Hypothesis 2

We will test the hypothesis that infants randomized to receive monthly DP between 2-24 months of age will have a lower incidence of malaria during the first 24 months of life compared to infants randomized to receive q 3 monthly DP. Secondary outcomes will include the incidence of complicated malaria, hospitalizations, adverse events, and the prevalence of anemia, asymptomatic parasitemia, and gametocytemia. This hypothesis will be limited to only infants born to mothers assigned to receive IPTp with 3 dose DP or monthly DP to ensure an equal balance of this prior phase of the interventions.

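### Through a broken cross-reference, the primary malaria-incidence analyses of Hypotheses 2, 3A and 3B take on a data-driven model choice that may end in a zero-inflated model, for which the only stated effect formula does not in general measure incidence

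*Protocol*

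**What the plan says.** Protocol 8.2.1 and 8.3.1 define the primary outcome of Hypotheses 2, 3A and 3B as incident malaria episodes divided by time at risk. That is an overall rate across all children in an arm.

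For Hypothesis 2, section 8.2.3 says: "We will compare the incidence of malaria using Poisson or negative binomial regression models as described in section 9.1.3". Section 8.3.3 uses the same reference for 3A and 3B. Section 9.1 is Record Keeping and has no subsection 9.1.3. The text that fits the reference is 8.1.3, under the secondary analyses of Hypothesis 1.

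Section 8.1.3 does three things:

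- It names Poisson or negative binomial regression, and gives the Poisson models a log follow-up-time offset.
- It states one effect measure: "We will translate the fitted coefficients and their confidence bounds into percentage effects with the formula" 100*[exp(coefficient)-1].
- It says overdispersion will be tested and variances adjusted. If the study data depart significantly from the required distributions, "we will employ negative-binomial or zero-inflated negative-binomial models to account for the observed pattern of data".

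It gives no threshold for the departure, no rule for choosing between the two fallback models, and no separate effect measure for the zero-inflated one.

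**The concern.** A Poisson or negative binomial coefficient on the log scale is a log ratio of overall rates, which is the outcome as defined. A zero-inflated negative binomial model splits the children into a group that can only have zero episodes and a group that follows a count distribution. Its count coefficient is the log rate ratio in the second group alone. If a regimen also changes the size of the first group, that part of its effect lies in the other half of the model and the stated formula does not pick it up.

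Two things are at stake. The reported percentage effect could describe a quantity other than the primary outcome. And the primary model for three hypotheses would be settled only after the trial data have been examined, by a criterion that the protocol does not state.

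**Working it through.** **1. The plan's own figures.** Table 10 uses "two-sided alpha = 0.05, power = 80"%, control incidence 3-5 episodes per person-year, and infant numbers of 90 vs 90 (Hypothesis 2), 90 vs 45 for each comparison (3A) and 162 vs 81 (3B). For a Poisson comparison of overall rates, solve for the relative difference d:

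(1.960 + 0.842) × sqrt[1/(n1·t·λ) + 1/(n2·t·λ·(1-d))] = -ln(1-d)

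With t = 1 person-year per child and no overdispersion:

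| Hypothesis | Stated | Recomputed (λ = 5 to λ = 3) |
|---|---|---|
| 2 | 18-23% | 17.9-22.8% |
| 3A | 22-28% | 22.1-28.2% |
| 3B | 16-21% | 16.6-21.3% (16.1-20.5% on the rate-difference scale) |

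The figures reproduce. They are relative differences in overall rates, so the trial is sized on the same quantity that 8.2.1 and 8.3.1 define.

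**2. What the formula measures under each model.** Let exp(b) be the count-part rate ratio, and π0 and π1 the structural-zero shares in the control and comparison arms.

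- Poisson or negative binomial: overall rate ratio = exp(b). The formula is right.
- Zero-inflated negative binomial: overall rate ratio = exp(b) × (1-π1)/(1-π0). The formula is right only if π1 = π0.

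The protocol gives no structural-zero shares, so those below are assumptions.

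| Count effect (what the formula gives) | π0 | π1 | Overall ratio | True incidence effect |
|---|---|---|---|---|
| -30% | 10% | 10% | 0.70 × 0.90/0.90 = 0.700 | -30.0% |
| -30% | 10% | 30% | 0.70 × 0.70/0.90 = 0.544 | -45.6% |
| -10% | 10% | 30% | 0.90 × 0.70/0.90 = 0.700 | -30.0% |
| 0% | 5% | 50% | 1.00 × 0.50/0.95 = 0.526 | -47.4% |

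A simulation of the second and third rows (90 per arm, 1.9 person-years, dispersion k = 0.4 assumed, 150 trials each) agrees. The negative binomial medians were -45.9% and -31.4%, against true effects of -45.6% and -30.0%. The zero-inflated count coefficients gave -30.7% and -13.0%. A sizeable share of the zero-inflated fits failed, so the closed form is the main evidence.

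**3. Is a data-driven choice needed?** Tables 1 and 2 of section 1.2 report the same endpoint at the same site. The variance of the log rate ratio implied by the printed 95% interval is [ln(upper/lower)/3.92]². The Poisson variance is 1/cases(control) + 1/cases(arm). Protective efficacies are first converted to rate ratios as 1-PE.

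| Comparison | Rate-ratio interval | Implied variance | Poisson variance | Ratio |
|---|---|---|---|---|
| Table 1, monthly SP | 0.72-1.19 | 0.01643 | 1/760 + 1/725 = 0.00270 | 6.1 |
| Table 1, daily TS | 0.56-0.93 | 0.01674 | 1/760 + 1/609 = 0.00296 | 5.7 |
| Table 1, monthly DP | 0.33-0.55 | 0.01698 | 1/760 + 1/366 = 0.00405 | 4.2 |
| Table 2, prior SP | 0.88-1.40 | 0.01403 | 1/670 + 1/689 = 0.00294 | 4.8 |
| Table 2, prior TS | 0.80-1.27 | 0.01390 | 1/670 + 1/678 = 0.00297 | 4.7 |
| Table 2, prior DP | 0.79-1.25 | 0.01370 | 1/670 + 1/659 = 0.00301 | 4.6 |

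Overdispersion of about 4-6 fold was known when the protocol was written. A model that allows for it can be named in advance.

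**The case against.** Several counter-arguments have force.

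- **Location.** The zero-inflated option stands under the secondary analyses of Hypothesis 1, and 8.2.3 and 8.3.3 themselves name only Poisson or negative binomial. This stands: that the primary analyses may become zero-inflated is an interpretation. It is the natural one, because no 9.1.3 exists and 8.1.3 opens with the same two model families before extending them. If it was not meant, the reference still has to be corrected.
- **The formula sits beside the Poisson text.** The protocol does not say that a zero-inflated count coefficient will be reported as the incidence effect, and a SAP might define another summary. This stands in part. The point is not an omitted detail: the protocol itself opens the data-driven switch and states a single effect measure.
- **Starting from Poisson is legitimate.** This stands. Section 8.1.3 allows variance adjustment, and Poisson regression with adjusted variance targets the stated rate ratio. A reader might infer from the overdispersion that beginning with Poisson is pointless; the text does not support that.
- **The switch is unlikely.** A reader might infer that effective monthly DP will produce excess zeros and so trigger the zero-inflated model. The protocol does not show this. A lower negative binomial mean gives more zeros without zero inflation. In simulated plain negative binomial data (assumed k = 0.4), AIC preferred a zero-inflated model with arm in the zero part in only 3-9% of trials. The earlier monthly DP arm still had 3.02 episodes per person-year.
- **A finding of no effect where incidence fell is an extreme.** It needs the whole effect to act through structural zeros, and nothing in the protocol supports that.
- **Maternal arm.** A reader might see its absence from the Hypothesis 2 model as a bias. Arms B-E are randomised 1:1:1:1 and Hypothesis 2 is restricted to them for balance, so leaving it out does not bias the rate ratio. Section 8.2.3 also permits adjustment.

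The described trigger is distributional fit, not the treatment result, and no inflation of type I error has been calculated or is claimed.

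**Conclusion.** The concern holds in a limited form. The reference to 9.1.3 is wrong. Read as 8.1.3, it lets the primary model for Hypotheses 2, 3A and 3B be chosen on the trial data from a set that includes one model whose count coefficient does not in general estimate episodes per time at risk. Moving from Poisson to negative binomial does no harm to the formula; only the zero-inflated option does, and only when structural-zero shares differ between arms.

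The size depends wholly on those shares, which are assumed here. The discrepancy is nil at 10% vs 10%. At 10% vs 30%, a count effect of -10% corresponds to an incidence effect of -30%, and one of -30% to -45.6%. How often the switch would occur is unknown. The overdispersion figures rest only on the protocol's printed intervals and case counts.

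**What to change.** - Correct the reference in 8.2.3 and 8.3.3 from 9.1.3 to 8.1.3.
- Name one primary model for Hypotheses 2, 3A and 3B: negative binomial regression with a log time-at-risk offset and robust standard errors. Poisson regression with the same offset and robust variance is equally acceptable. The formula 100*[exp(coefficient)-1] then stays as written.
- Limit any zero-inflated model to a sensitivity analysis, reported as the ratio of overall mean incidence between arms.
- Optionally, include maternal arm as a factor in Hypothesis 2 for precision.

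The cost is protocol or SAP wording; sample size and conduct are untouched. The downside is a small loss of flexibility should the negative binomial fit poorly, which the robust standard errors cover.
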